LA: Left atrial

CONFIDENTIAL

This material is the property of the University of Pennsylvania.

Study Summary

Title	Prospective Elimination Of Distal Coronary Sinus-Left Atrial Connections for Atrial Fibrillation Ablation Trial
Short Title	PRECAF Trial
IRB Number	
Protocol Number	
Phase	Pilot Study.
Methodology	Randomized; Single blind.
Study Duration	2 years
Study Center(s)	Single-center
Objectives	To examine the efficacy of targeting connections between coronary sinus and left atrium during an ablation procedure in addition to pulmonary vein (PV) isolation and non-PV triggers in Atrial fibrillation patients.
Number of Subjects	100 subjects are expected to be enrolled. An interim analysis will be performed after enrollment of 50 patients.
Main Inclusion and Exclusion Criteria	
Inclusion criteria are:
 
● Patients with paroxysmal or persistent atrial fibrillation; AND● Undergoing first AF ablation; AND● Age ≥ 18 years. 
Patients are not eligible if they have any of the following exclusion criteria:
 
● Previous left atrial ablation;● Women currently pregnant;● Mental or physical inability to take part in the study;● Known terminally ill patients.

Investigational Product (drug, biologic, device, etc.)	
For Device include the planned use	N/A
For Drug, food, cosmetic, etc. include the dose, route of administration and dose regimen	N/A
Duration of administration (if applicable)	N/A
Reference therapy	The reference therapy is pulmonary vein isolation and elimination of non-PV triggers. The investigational arm will include pulmonary vein isolation and non-PV trigger elimination, in addition to distal coronary sinus isolation.
Statistical Methodology	The primary efficacy analysis will be performed among the intent-to-treat study groups using Cox-regressions and Kaplan-Meier curves to compare time to the initial occurrence of AF after the blanking period following AF ablation.
Safety Evaluations	
Occurrence of one or more of the following events during the 30 day period following the ablation procedure:
 
 1. stroke, 2. myocardial infarction, 3. esophageal injury, 4. pulmonary vein stenosis, 5. bleeding, 6. heart failure, and 7. death.

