3.2.3 Primary Safety Endpoints [if applicable]

The primary safety composite outcome is defined by occurrence of one or more of the following events during the 30-day period following the ablation procedure: stroke, myocardial infarction, esophageal damage, pulmonary vein stenosis, bleeding, heart failure and death.

4 Study Population and Duration of Participation

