4.4 Duration of Study Participation

Participants will be part of the study for 6 months after ablation.

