4.5 Total Number of Subjects and Sites

Recruitment will end when 100 participants are enrolled at Penn.

4.6 Vulnerable Populations:

Vulnerable populations will not be targeted.

5 Study Intervention

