7.6 Safety Evaluations

Comparing study adverse outcomes between the two study groups will be utilized to assess the safety of the additional ablation lesions in the investigational arm.

8 Statistical Plan

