8.1 Primary Endpoint

The primary endpoint is the recurrence of atrial arrhythmia post-ablation. The primary endpoint is defined as a non-self-terminating (>30 seconds) episode of atrial fibrillation, atrial flutter, or atrial tachycardia demonstrated by ECG or 30 day monitors after the 90-day post-ablation blanking period.

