8.3 Sample Size and Power Determination

Assuming alpha 0.05, power 0.80, and 1:1 randomization of 100 participants, and 0.7 probability of AF freedom in the control group, we will resolve a 2-sided minimum experimental arm hazard ratio of 0.2 with implementation of the log-rank test.

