9.6 Stopping Rules

N/A

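### Does the undescribed interim analysis at 50 patients break the two-sided 0.05 of the final log-rank test?

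*Combined protocol and SAP*

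**What the plan says.** The interim appears once, in the Number of Subjects row of the Study Summary: "An interim analysis will be performed after enrollment of 50 patients". Section 8 (Statistical Plan) does not return to it. Section 8.3 sizes the trial on a single test: "Assuming alpha 0.05, power 0.80, and 1:1 randomization of 100 participants", with 0.7 AF freedom in controls and a detectable hazard ratio of 0.2. The entry under "9.6 Stopping Rules" is N/A. Section 4.5 states "Recruitment will end when 100 participants are enrolled at Penn".

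Two kinds of outcome could be examined at such a look. The safety composite in 3.2.3 is "one or more of the following events during the 30-day period following the ablation procedure", and 7.6 already plans a by-arm comparison: "Comparing study adverse outcomes between the two study groups will be utilized to assess the safety of the additional ablation lesions". The primary endpoint in 8.1 counts only arrhythmia "demonstrated by ECG or 30 day monitors after the 90-day post-ablation blanking period", and 4.4 says "Participants will be part of the study for 6 months after ablation".

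On access to assignments, 3.1.4 has the study coordinator hold the master list. Section 5.6 blinds the participant and the team other than the coordinator and the patient's own investigator. Sections 3.1.3 and 7.5 blind the two adjudicators. Section 9.7 gives safety oversight to the principal investigator with co-investigators.

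**The concern.** An announced interim with no alpha plan, beside a sample size that uses all of 0.05 at the end, is the usual setting for an unadjusted second chance to claim success. If the treatment arms were compared on recurrence at 50 patients and again at 100, each at 0.05, the stated error rate would not hold.

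The trigger also fits the primary endpoint poorly. It counts enrollments, whereas primary events start only after day 90 and are sought mainly by the last-month monitor. And since no recipient is named, a by-arm table might reach staff whom 5.6 keeps blinded.

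The pilot label alone does not answer this, because 8.3 states a powered two-sided test.

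**Working it through.** **1. The plan's own figure.** Inputs from 8.3: 50 per arm, control event probability 1 − 0.7 = 0.30, hazard ratio 0.2.

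- Expected events: 50 × 0.30 + 50 × (1 − 0.7^0.2) = 15.00 + 3.44 = 18.44.
- Freedman drift: √18.44 × (1 − 0.2)/(1 + 0.2) = 4.294 × 0.667 = 2.863.
- Power: Φ(2.863 − 1.960) = 0.817.

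The stated 80% power is reproduced by one final test at the full 0.05. No alpha is set aside for an earlier look.

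**2. The plan as written.** Let Z1 be any interim statistic and Z2 the final log-rank statistic. If the efficacy conclusion rests on Z2 alone and recruitment runs to 100 regardless of Z1, the type I error is P(|Z2| > 1.96) = 0.05. Looking at Z1 does not alter that. Error is added only if |Z1| > 1.96 may itself count as success.

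**3. The reading that would inflate error.** With success claimable at either look, the error is 1 − P(|Z1| < 1.96, |Z2| < 1.96), where the correlation is √t and t is the information fraction. This gives 0.083 at t = 0.50, 0.091 at t = 0.25 and 0.093 at t = 0.17.

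**4. What data the look would have.** Accrual is not stated. The 2-year duration less 6 months of participation suggests 18 months if the 2 years include follow-up; 12 and 24 months show the range. Even accrual over A months puts the 50th enrollment at A/2. The number of the 50 with at least m months of follow-up is then (A/2 − m) × 100/A. For A = 18 and m = 6 this is 3 × 100/18 = 16.7.

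The table takes ablation on the day of enrollment. Events and error come from null log-rank simulations with 30% event risk in both arms (100 × 0.30 = 30 events in total). Events fell either across months 3–6 or only in months 5–6. The error column applies only under the reading in step 3.

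| Accrual (months) | Completed 6 months | Past day 90 | Past day 30 | Mean primary events at look | Overall error |
|---|---|---|---|---|---|
| 12 | 0 | 25 | 42 | 1.1–3.8 | 5.7–8.6% |
| 18 | 17 | 33 | 44 | 5.5–7.5 | 8.6–9.4% |
| 24 | 25 | 38 | 46 | 7.8–9.3 | 8.7–9.4% |

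Consent may precede ablation (3.1.1, 12.4). A lag of one or two months lowers the 18-month figure to 7.4–9.2%. With 12 months of accrual and a one-month lag it is about 5–7%. The low values arise because a handful of events seldom reaches significance: with balanced risk sets and all d events in one arm, Z = (d/2)/√(d/4) = √d, so at least four events are needed.

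**5. Which reading the text supports.** At the trigger, 42 to 46 of 50 patients would be past day 30, against 0 to 25 with complete primary follow-up. An enrollment trigger therefore suits the 30-day composite, which 7.6 already compares by arm. The N/A in 9.6 and the fixed end of recruitment in 4.5 point the same way.

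**The case for a change.** The strongest reply is that the absence of a stopping rule does not forbid an efficacy claim. Nothing in the document bars the team from testing recurrence at 50 patients and publishing a positive result, the stated objective is efficacy, and section 14 plans publication. One sentence would remove the doubt at almost no cost.

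Part of this stands. The Study Summary line is the only text on the look, and neither redaction nor text extraction explains the silence. The conditional arithmetic is also sound. But the argument turns on what someone might do outside the plan. Claiming success at 50 would mean acting on a rule the plan does not contain, in a trial that says it recruits to 100. The sentence asked for would describe the look; it would not alter the final test, its level or the sample size.

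The blinding point is weaker. The document does not name who sees interim results, but it sends by-arm data to nobody who is meant to be blinded. The coordinator who holds the assignments can prepare a by-arm table, and the adjudicators are explicitly blinded. That is silence, not a breach.

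**Conclusion.** The concern does not call for a change. As written, the trial has no early-success rule, recruits to 100 and makes one powered comparison, so the two-sided 0.05 in 8.3 holds. Inflation to roughly 8–9% needs three unstated conditions together, plus an assumed 18-month accrual with little delay between enrollment and ablation. With 12-month accrual it runs from no inflation to about 9%, depending on event timing and delay. What is left is an undescribed look, which an analyst would sensibly treat as descriptive or as a check on 30-day safety. This conclusion rests on the final log-rank test remaining the only basis for an efficacy claim. If the team declared success at 50 patients, the inflation figures above would apply to that decision.

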In canine hearts, the coronary sinus musculature is electrically connected to the right atrium (RA) and the left atrium (LA) which forms an RA-LA connection.⁴

1.2.2 *Clinical Data to Date*

In prior work, we sought to describe the prevalence and variability of coronary sinus (CS) and left atrial (LA) myocardium connections, their susceptibility to rate-dependent conduction block, and association with atrial fibrillation (AF) and flutter induction. The study cohort included 30 consecutive AF patients (age 63.3 \pm 10.5 years, 63% male). Multipolar catheters were positioned in the CS, high right atrium (HRA), and LA parallel to and near the CS. Trains of 10 pacing stimuli were delivered during sinus rhythm from each of the following sites: CS proximal (CSp), CS distal (CSd), LA septum (LAs), lateral LA (LAI), and HRA, at the following cycle lengths: 1000, 500, 400, 300, and 250 ms, while recording from the other catheters. With the CS 9 to 10 bipole just inside the CS ostium, CS-LA connections were observed in 100% at CS 9 to 10, 30% at CS 7 to 8, 23% at CS 5 to 6, 23% at CS 3 to 4, and 97% at CS 1 to 2. Eighteen patients (60%) had AF/atrial flutter induced. Rate-dependent conduction block of a CS-LA connection at cycle length of \geq 250 ms was present in 17 (94%) of those with versus none of those without AF/atrial flutter induction ($P<0.001$). We concluded that rate-dependent eccentric CS-LA conduction block is associated with AF/atrial flutter induction in patients with drug-refractory AF undergoing ablation. The presence of dual muscular CS-LA connections, coupled with unidirectional block in one limb, seems to serve as a substrate for single or multiple reentry beats, and arrhythmia induction. (Huang, D. et al. Association of Rate-Dependent

CONFIDENTIAL

Conduction Block Between Eccentric Coronary Sinus to Left Atrial Connections With Inducible Atrial Fibrillation and Flutter. Circ Arrhythm Electrophysiol. 2017 Jan;10(1)).

Importantly, 4 patients in the above study cohort, with AF/AFL induction after rate-dependent CS-LA conduction block, the connection site was targeted from the endocardial LA surface. These were distal CS to lateral LA connections. The CS-LA connection was successfully and safely ablated in all 4 cases. Repeating the identical pacing protocol after ablation failed to induce any arrhythmia in these cases (Circ Arrhythm Electrophysiol. 2017 Jan;10(1)).

1.2.2.1 Human Pharmacokinetics

N/A

1.2.2.2 Clinical Studies in Adults

The study will enroll only adults patients aged > 18 years.

1.2.3 Clinical Studies in Children

No children will be enrolled in this study.

1.3 Dose Rationale (if applicable)

N/A

2 Study Objectives

2.1 Primary Objective

To examine the efficacy of targeting connections between coronary sinus and left atrium during an ablation procedure in addition to standard pulmonary vein (PV) isolation and non-PV triggers elimination.

3 Investigational Plan

3.1 General Design

The study is designed as a randomized, single-blind, small scale pilot study. Expected duration of subject participation is six months. A 30-day event monitor will be used for the first month after ablation. Then, regular clinic visits at 6 weeks and 6 months will be arranged after ablation with 12 lead electrocardiogram check-up. In the last month, a 30-day event monitor will be set to detect the recurrence of atrial arrhythmias.

3.1.1 Screening Phase

Participants will be recruited in the cardiology clinic at the Hospital of the University of Pennsylvania or satellite sites. The protocol will be explained to those who are indicated for atrial fibrillation ablation. Eligible participants will be identified according to the inclusion/exclusion criteria section of the protocol. Written consent will be obtained before the ablation procedure.

3.1.2 Study Intervention Phase

Participants will be randomized in a 1:1 fashion to 2 groups. Group 1 participants will undergo the current standard of care ablation with pulmonary vein isolation and non-pulmonary vein triggers elimination; group 2 participants will undergo coronary sinus-left atrium connection ablation, in addition to pulmonary vein isolation and non-pulmonary vein triggers. The distal coronary sinus electrode pair will be paced at an output not higher than 10mA. During pacing, the earliest activation time in the left atrium at 20 plus milliseconds after the pacing spike will be localized and targeted for ablation. Lesions will be delivered at 40 watt or less, for 30 seconds or less and titrated down using standard criteria at the discretion of the proceduralist. Stimulation for induction of AF with pacing cycle length from 250 to 180 ms or 2:1 capture

CONFIDENTIAL

will be performed from proximal coronary sinus and distal coronary sinus and at the site of left atrial to CS connection before and after ablation.

3.1.3 Follow Up Phase

A 30-day event monitor will be used for the first month after ablation. Then, regular clinic visits at 6 weeks and 6 months will be arranged after ablation with 12 lead electrocardiogram check-up. In the last month, a 30-day event monitor will be set to detect the recurrence of atrial arrhythmias. An adjudication committee consisting of two electrophysiologists that are blinded to the randomization scheme will review AF events. Time to first AF episode will be recorded as the primary outcome.

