5.6 Blinding

The unblinded research coordinator will keep a master file of participant assignments. Once a participant is randomized, the investigator/clinician for the patient will be notified of the participant assignment. The remainder of the research team and the participant will be blinded to participant assignment.

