9.1 Definitions

9.1.1 Adverse Event

An **adverse event (AE)** is any symptom, sign, illness or experience that develops or worsens in severity during the course of the study. Intercurrent illnesses or injuries will be regarded as adverse events. Abnormal results of study procedures will be considered to be adverse events if the abnormality:

- results in study withdrawal
- is associated with a serious adverse event
- is associated with clinical signs or symptoms
- leads to additional treatment or to further diagnostic tests
- is considered by the investigator to be of clinical significance

Additionally, any untoward medical occurrence associated with ablation near the coronary sinus will be considered an adverse effect.

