9.2 Recording of Adverse Events

At each contact with the subject, the investigator will seek information on adverse events by specific questioning and, as appropriate, by examination. Information on all adverse events will be recorded immediately in the source document, and also in the appropriate adverse event module of the case report

CONFIDENTIAL

form (CRF). All clearly related signs, symptoms, and abnormal diagnostic procedures results will be recorded in the source document, but grouped under one diagnosis.

All adverse events occurring during the study period will be recorded. The clinical course of each event will be followed until resolution, stabilization, or until it has been determined that the study intervention or participation is not the cause. Serious adverse events that are still ongoing at the end of the study period will be followed up to determine the final outcome. Any serious adverse event that occurs after the study period and is considered to be possibly related to the study intervention or study participation will be recorded and reported immediately.

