9.3 Relationship of AE to Study

The principal investigator will characterize the relationship of each adverse event to the study procedures as definitely related, probably related, possibly related, unlikely or unrelated.

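### The judgement-dependent components of the primary safety composite have no criteria and no blinded review, although a blinded committee already exists for AF events

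*Combined protocol and SAP*

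**What the plan says.** All references are to the combined protocol and SAP.

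- **The safety outcome.** Section 3.2.3 counts a participant who has one or more of these within 30 days of ablation: "stroke, myocardial infarction, esophageal damage, pulmonary vein stenosis, bleeding, heart failure and death". No criteria are given for any item. The Study Summary lists the same seven, calling the esophageal item injury rather than damage.
- **Its use.** Section 7.6 assesses the safety of the extra lesions by comparing adverse outcomes between the two groups.
- **Who asks.** Section 9.2: "At each contact with the subject, the investigator will seek information on adverse events by specific questioning". Section 10.2 adds that study data come from the EMR and clinic notes.
- **Who knows the arm.** Section 5.6 states that after randomization "the investigator/clinician for the patient will be notified of the participant assignment". It continues: "The remainder of the research team and the participant will be blinded to participant assignment".
- **What is reviewed blind.** Section 3.1.3: "An adjudication committee consisting of two electrophysiologists that are blinded to the randomization scheme will review AF events". Section 7.5 repeats this for the AF ECG data. No section gives these reviewers any safety event.
- **Other oversight.** The principal investigator and co-investigators oversee safety (9.7). Stopping rules (9.6) and the study monitoring plan (11.1) are marked not applicable.

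**The concern.** The added lesions cannot be concealed from the operator, but outcome assessment can be blinded, and the plan does this for AF recurrence. It does not do so for the outcome meant to show whether the extra lesions are safe. An investigator who knows that a patient had ablation near the coronary sinus may probe harder for complications, or may be slower to label a borderline finding as one. Without criteria for bleeding, heart failure or esophageal damage, nothing in the plan limits how far that knowledge can affect the count. The between-arm comparison in 7.6 could then show a difference that is not real, or hide one that is.

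**Working it through.** **1. The two outcomes side by side**

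| | AF recurrence | Primary safety composite |
|---|---|---|
| Event criteria | Rhythm, duration over 30 seconds, after a 90-day blanking period (3.2.1, 8.1) | Seven named items, no criteria (3.2.3) |
| Source | ECGs and 30-day monitors (7.5) | Investigator's questioning (9.2); EMR and clinic notes (10.2) |
| Blinded review | Two blinded electrophysiologists (3.1.3, 7.5) | None stated |
| Compared between arms | Yes (8.4.2) | Yes (7.6) |

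**2. Which components are exposed.** Death is hardly open to this bias. Stroke, myocardial infarction and pulmonary vein stenosis are less open to it than the rest. Bleeding, heart failure and esophageal damage depend most on who asks and where the line is drawn.

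**3. Which routes can move the composite.** The composite counts occurrence only.

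- *Asking* (9.2): can move it. Someone who knows the arm may look harder in one arm.
- *Classifying a borderline event*: can move it, because no criteria exist.
- *Relatedness* (9.3): cannot move it. An event counts whether or not it is judged related.
- *The coronary sinus sentence* (9.1.1): cannot move it. A bleed counts wherever the lesion was.

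**4. Size per event.** The plan gives no safety figure to reproduce; the hazard ratio of 0.2 in 8.3 concerns efficacy only. The inputs used are 100 participants and 1:1 allocation (8.3).

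- Per arm: 100 / 2 = 50.
- One event classified differently: 1 / 50 = 2 percentage points.

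Illustration, assuming a true rate of 10% in both arms (5/50 each):

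- two events missed in group 2: 5/50 v 3/50 = 10% v 6%;
- two extra events counted in group 2: 5/50 v 7/50 = 10% v 14%.

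**5. A range.** Assume equal true risk in both arms, extra events recorded in group 2 only, and a two-sided Fisher test at 0.05. The plan names no test for safety, so the test is also an assumption. Expected events are 50 × rate.

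| True rate (assumed) | Extra recorded in group 2 | Expected events, group 1 v 2 | Apparent risk ratio | Chance of p<0.05 |
|---|---|---|---|---|
| 5% | 0 | 2.5 v 2.5 | 1.0 | 0.7% |
| 5% | 5 points | 2.5 v 5.0 | 2.0 | 6.3% |
| 5% | 10 points | 2.5 v 7.5 | 3.0 | 24.4% |
| 10% | 0 | 5.0 v 5.0 | 1.0 | 1.8% |
| 10% | 5 points | 5.0 v 7.5 | 1.5 | 6.1% |
| 10% | 10 points | 5.0 v 10.0 | 2.0 | 19.5% |

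A handful of events would seldom produce a significant result, but it would visibly distort the estimate. The table shows over-recording; under-recording in group 2 would bias the comparison the other way.

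**The case against.** The strongest reply has four parts.

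*This is a single-center pilot with no powered safety hypothesis.* True, and it limits the severity. But 7.6 still rests a conclusion on the comparison, and with few events each classification carries weight.

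*Exposure is limited.* Participants are blinded, which limits differential reporting, and the EMR offers a second source. Both points stand. Neither prevents differential asking or classification. It is also fair that 5.6 unblinds an investigator with certainty only for his or her own patients. The principal investigator may be blinded for the others.

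*Missing criteria are a separate fault.* They would matter even under perfect blinding. That is correct. They are raised here because, without them, knowledge of the arm has more room to act, and because a committee needs criteria to work from.

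*Two electrophysiologists are not obvious judges of stroke, bleeding or esophageal injury, and procedure reports may reveal the arm.* Both are real limits. Prespecified criteria reduce the first; the second can only be reduced.

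A reader might also infer that two further provisions bias the composite: "The principal investigator will characterize the relationship of each adverse event to the study procedures" (9.3), and "any untoward medical occurrence associated with ablation near the coronary sinus will be considered an adverse effect" (9.1.1). The documents do not support this, because the composite counts occurrence regardless of cause. Nor is the 9.1.1 sentence strictly confined to group 2: group 1 also receives non-PV trigger elimination (3.1.2), and nothing bars that from the same region. The general definition in 9.1.1 already covers both arms broadly. These provisions can affect attribution of adverse events in general, but not the composite.

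**Conclusion.** The point holds for elicitation and classification of the judgement-dependent components of the 30-day composite. They have no criteria and no blinded review, and they are sought by an investigator who knows the arm for his or her own patients. This rests on reading the investigator who asks in 9.2 as being, at least for some contacts, the one told the arm under 5.6.

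The size is 2 percentage points per differently classified event, with 50 per arm. Everything beyond that is illustration on assumed rates: the documents give no safety event rate, and the likely amount and direction of bias are unknown. A reader might take the 10% v 6% or 10% v 14% figures as a forecast; they are not. The primary efficacy endpoint and the sample size are unaffected. This is a cheap improvement, not a flaw that invalidates the trial.

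**What to change.** - **3.1.3, 7.5 and 7.6:** extend the remit of the same two blinded electrophysiologists to every candidate component of the 30-day composite, with one prespecified set of event criteria for both arms. Redact arm and lesion location from the source packets as far as possible.
- **9.2:** use the same adverse event checklist in both arms. The committee can correct how events are classified, but it cannot recover events that were never asked about.
- **9.1.1:** keep the coronary sinus sentence, since 12.1 identifies a higher coronary risk in that region. Add that untoward occurrences associated with any part of the ablation procedure, in either arm, are recorded in the same way.

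The cost is protocol wording, preparing redacted packets and modest extra review time for a committee that already exists. Some procedure reports will not be fully masked. No patients, visits or procedures are added, and the sample size does not change.
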